6.2 Other treatment(s)

6.2.1 Concomitant therapy

The investigator must instruct the subject to notify the study site about any new medications the subject takes after signing the study informed consent. All medications, procedures and significant non-drug therapies (including physical therapy and blood transfusions) administered after the subject was enrolled into the study must be recorded in the appropriate Case Report Forms.

Each concomitant drug/procedure must be individually assessed against all exclusion criteria/prohibited medication. If in doubt the investigator should contact the sponsor before randomizing a subject or allowing a new medication to be started. If the subject is already enrolled, contact the sponsor to determine if the subject should continue to take study treatment or should discontinue study treatment but still continue participation in the study.

6.2.1.1 Permitted concomitant therapy requiring caution and/or action

Fellow eye

During the study, standard of care or other treatments according to the investigator's practice for nAMD and other diseases in the fellow eye are permitted at any time and must be recorded in the appropriate eCRF page. Treatment of the fellow eye must be scheduled in a way not to disturb the schedule for visits and treatments in the study eye. The fellow eye must be monitored according to routine practice and adverse events (AEs) captured in the eCRF.

Study eye

Administration of topical ocular corticosteroids in the study eye is allowed during the study. Corticosteroids administered via intra-nasal, inhaled, intra-articular or non-extensive dermal route (< 20% total body surface area) are also permitted during the study. For other routes of corticosteroid administration, refer to [Section 6.2.2](#). If cataract surgery is necessary and cannot be postponed until end of study, attempt to schedule cataract surgery \geq 7 days after the most recent study treatment. Study treatment may be resumed \geq 14 days after cataract surgery, assuming an absence of surgically-related complications.

If yttrium aluminum garnet (YAG) laser is necessary, it should be performed \geq 7 days prior to the scheduled study visit.

Ideally, while adhering to the visit schedule specified in the protocol, study drug should be administered at least 7 days before or after SARS-CoV-2 vaccinations. This will allow time to separate potential drug-drug interactions and side effects caused by vaccination. This 7-day time window would also be recommended for the first study treatment at the baseline visit.

6.2.2 Prohibited medication

Use of the treatments displayed in the below table ([Table 6-2](#)) are not allowed after screening.

Table 6-2 Prohibited medications and procedures

Medication/Procedures	Prohibition period	Action taken
Study eye		
Any periocular injection or intraocular administration of corticosteroids (except if needed as short-term treatment of AE)	Anytime	Discontinue study treatment (except if for treatment of AE)
Anti-VEGF therapy other than assigned study medication	Anytime	Discontinue study treatment
Panretinal laser, PDT laser, nanosecond laser or focal laser photocoagulation with involvement of the macular area	Anytime	PD documentation and continuation of study treatment at the investigators discretion
Any investigational drug, biologics or device	Anytime	Discontinue study treatment
Systemic		
Anti-VEGF treatment	Anytime	Discontinue study treatment
Any investigational drug, biologic or device	Anytime	Discontinue study treatment
Medications known to be toxic to the lens, retina or optic nerve, including ethambutol, chloroquine/hydroxychloroquine, deferoxamine, phenothiazines and tamoxifen (except temporary use for COVID-19 treatment)	Anytime	Discontinue study treatment

Standard of care or other treatments according to the investigator's practice for nAMD and other diseases in the fellow eye are permitted at any time and must be recorded in the appropriate eCRF page.

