6.2.3 Rescue medication

There will be no rescue medication for nAMD in the study eye.

In case of lack of efficacy with investigational drug for nAMD and if the investigator deems it is in the best interest of the patient to receive prohibited treatment ([Section 6.2.2](#)) in the study eye, the investigator should follow the instructions for study treatment discontinuation or study discontinuation provided in [Section 9](#).

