9.1.1 Discontinuation of study treatment

Discontinuation of study treatment for a subject occurs when study treatment is stopped earlier than the protocol planned duration and can be initiated by either the subject or the investigator.

The investigator must discontinue study treatment for a given patient if, he/she believes that continuation would negatively impact the subject's well-being.

Study treatment must be discontinued under the following circumstances:

- Subject decision
- Pregnancy (see [Section 8.4.2](#) and [Section 10.1.4](#))
- Use of prohibited treatment (see [Section 6.2.2](#))
- Any situation in which continuation with study treatment might result in a safety risk to the subject
- Unsatisfactory therapeutic effect, e.g. a subject requires injections more frequently than every 8 weeks after the loading phase (week 8, loading arm) or baseline (non-loading arm).
- Subjects develop intraocular inflammation, retinal vasculitis and/or retinal vascular occlusion

If discontinuation of study treatment occurs, the investigator should make a reasonable effort to understand the primary reason for the subject's premature discontinuation of study treatment and record this information on the appropriate eCRF page.

Subjects who prematurely discontinue study treatment for any reason, except for withdrawal of consent (refer to [Section 9.1.2](#)), should continue in the study with all the scheduled visits and assessments (except disease stability assessment, administration of study treatment, post-injection assessment and adherence to prohibited medication list) until EOS. These patients can be switched to standard of care anti-VEGF IVT as per investigator's discretion. Any IVT injection is contraindicated in subjects with active intraocular or periocular infections and in subjects with active intraocular inflammation; therefore, the investigators must verify that these conditions are not present in the study eye prior to every injection.

Subjects who decide not to participate in the study further should NOT be considered withdrawn from the study, UNLESS they withdraw their consent (see [Section 9.1.2](#)). **Where possible, subjects should return for the EOS visit assessments to be performed as scheduled in Table 8-1.**

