5.4 Statistical models

5.4.1 Primary analysis

1) SAS-Code for **mixed model for repeated measures (MMRM)**:

Estimates for the primary objective ("Mean change in BCVA from baseline to mean of visits at week 40 to week 52 (Visit 11 to 14)") and the secondary objective ("Mean change in BCVA from baseline to mean of visits at week 16 to week 28 (Visit 5 to 8)") in one single model:

```
proc mixed alpha=0.1;
  where fasfl=Y and trteyen=1;
  where 2 le avisitn le 14;
  class subjid trtan avisitn;
  model chg = base age trtan avisitn trtan*avisitn /ddfm=kr;
  repeated avisitn / sub = subjid type = un;
  lsmeans trtan*avisitn /slice = avisitn cl ;
  estimate 'Treatment difference averaged over week 40 to week 52'
    trtan -1 1
    trtan * avisitn
      0 0 0 0 0 0 0 0 -0.25 -0.25 -0.25 -0.25
      0 0 0 0 0 0 0 0 0.25 0.25 0.25 0.25/cl;
  estimate 'Treatment difference averaged over week 16 to week 28'
    trtan -1 1
    trtan * avisitn
      0 0 0 -0.25 -0.25 -0.25 -0.25 0 0 0 0 0 0
      0 0 0 0.25 0.25 0.25 0.25 0 0 0 0 0 0/cl;
run;
```

3) SAS-Code for **logistic regression** model:

- Secondary endpoint: "rate of patients (overall and per treatment arm) with prolonged interval (*intlong*) compared to mean treatment interval in last 24 weeks prior to enrollment"

```
proc logistic descending alpha=0.05;
  where fasfl=Y;
  class trtan;
  model intlong = base age trtan;
run;
```

- Secondary endpoint: "proportions of patients maintained at a q12w interval from baseline / upload to week 52"

```
proc logistic descending alpha=0.05;
  where fasfl=Y;
  class trtan;
  model q12w = base age trtan;
run;
```

where 'maintained at a q12w interval' (q12w = Yes) is defined as DAA = q12w in all visits AND no treatment discontinuation.

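### Protocol Table 6-2 leaves continuation after prohibited study-eye laser or PDT to the investigator, while Section 9.1.1 requires discontinuation; the q12w-maintenance result depends on which is followed

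*Protocol*

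**What the plan says.** Protocol 6.2.2 states that the treatments in Table 6-2 "are not allowed after screening". One study-eye row covers "Panretinal laser, PDT laser, nanosecond laser or focal laser photocoagulation with involvement of the macular area", prohibited at any time. Its action column reads "PD documentation and continuation of study treatment at the investigators discretion". Most other rows simply say to discontinue study treatment. The steroid row says the same, with an exception for treating an adverse event.

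Protocol 9.1.1 opens its list with "Study treatment must be discontinued under the following circumstances". One entry is use of prohibited treatment, with a cross-reference to 6.2.2 and no exception for any row.

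Protocol 6.2.3 covers a narrower case. If the drug lacks efficacy and the investigator wants to give a prohibited treatment in the study eye, "the investigator should follow the instructions for study treatment discontinuation or study discontinuation" set out in Section 9.

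Protocol 6.2.1 tells the site to contact the sponsor about whether an enrolled subject should stay on study treatment, but states no rule.

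In SAP 5.4.1, being maintained at q12w "is defined as DAA = q12w in all visits AND no treatment discontinuation". Table 2 in SAP 2.7.2 scores patients who stop treatment before week 52 as non-responders.

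**The concern.** For one and the same event, one current section makes stopping optional and another makes it mandatory. Neither statement comes from the amendment log. Sites could follow different sections in good faith. Treatment is open to the investigator (Protocol 6.4), so the choice is made knowing the arm. About 50 patients are spread over about 33 centers (Protocol 3), roughly 1.5 per center, so almost every such decision would rest on a different site's reading.

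The site's decision then passes into a secondary endpoint that the SAP models by logistic regression. With arms of about 25, a single patient is visible in the result. Two patients with identical disease-activity records could fall on opposite sides of the endpoint for a reason unrelated to the durability of the regimen.

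**Working it through.** **Do the passages conflict?**

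1. Is macular laser or PDT a prohibited treatment in the sense of 9.1.1? Yes. Section 6.2.2 calls everything in Table 6-2 a treatment that is not allowed, and 9.1.1 points to 6.2.2.
2. What does 9.1.1 require? Discontinuation, without qualification.
3. What does the Table 6-2 row require? Documentation of a deviation, with continuation left to the investigator.
4. What does 6.2.3 add? Only where the laser is given for lack of efficacy, it sends the investigator to Section 9, and so to the mandatory list. It says nothing about laser given for another reason.
5. Is there a precedence rule? None is stated. The adverse-event exception in the steroid row meets the same unqualified wording in 9.1.1, although there the exception is also written into the description of the prohibited item and is easier to read around.

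**How does the decision reach the endpoints?**

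Take a patient who has Table 6-2 laser, whose disease-activity assessment is q12w at every visit, and who has no other reason to stop.

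| Site follows | Study treatment | q12w maintenance (SAP 5.4.1, 2.7.2) |
|---|---|---|
| Table 6-2, and continues | continues | responder |
| 9.1.1 | stopped | non-responder |

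If any assessment is q8w, or the patient would have stopped anyway, both rows give non-responder and the conflict has no effect on this endpoint.

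Interval prolongation (SAP 2.7.2) compares the last two brolucizumab injections with the pre-study mean interval, and counts a patient with one injection as not prolonged. Discontinuation matters here only when it is early:
- A non-loading patient stopped before the week 12 injection has one injection and is automatically not prolonged.
- A loading patient stopped after week 8 and before the next injection has a last interval of about 4 weeks, where continuing on q12w would have given 12.
- A patient stopped after a 12-week interval keeps that interval.

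The primary BCVA analysis follows a treatment policy (SAP 2.5.3), so data are kept whether or not treatment stops.

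**Size.** The inputs are 25 per group expected and 23 per group at the time of the amendment, with an SD of 13 letters (Protocol 12.8.1). The only design figure there is the confidence-interval half-width, and it reproduces: 1.96 × 13 × √(2/25) = 7.21 and 1.96 × 13 × √(2/23) = 7.51. This point does not depend on it; only the group sizes are used.

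The shift in an arm's q12w proportion from k affected patients is k/n. The documents give no laser rate, so k from 1 to 3 in one arm is an assumption:

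| k | n = 25 | n = 23 |
|---|---|---|
| 1 | 4.0 points | 4.3 points |
| 2 | 8.0 points | 8.7 points |
| 3 | 12.0 points | 13.0 points |

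If the affected patients are all in one arm, the difference between arms moves by the same amount.

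**The case against.** The strongest reply is that the sections fit together as a general rule and a schedule. Section 9.1.1 cites 6.2.2, and the table there gives an action for each row, so the row's action governs. This is a plausible reading, and it means one cannot say that no interpretation satisfies both passages. But it has to be supplied by the reader: 9.1.1 is mandatory in form and does not defer to the table's actions.

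Other parts of the reply stand and limit the point:

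- The sponsor-contact route in 6.2.1 gives some central control over doubtful cases, though no rule.
- A reader might take 6.2.3 as a second general instruction to stop after any laser. It applies only to lack of efficacy and leads back to Section 9, so it is not independent support.
- A reader might infer that sites score the endpoint differently. They do not. The SAP applies one rule to everyone; what differs is the treatment decision fed into it.
- A reader might infer that every laser-treated patient moves the proportion by 4 points. That holds only under the conditions set out in the working.
- If the sponsor settles on investigator discretion, management could still differ between patients. Reconciliation would then remove the contradiction but not that variation.

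**Conclusion.** The inconsistency is real, lies in current text, and is of low severity. Table 6-2 and 9.1.1 give different instructions for study treatment after prohibited study-eye laser or PDT, with no stated precedence. The consequence falls on q12w maintenance and on discontinuation counts, and occasionally on interval prolongation when stopping is early. Each patient who meets the conditions is worth 4.0 points of an arm's q12w proportion at 25 per arm, or 4.3 at 23. Few are likely, and the range of 1 to 3 per arm is assumed.

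It would be wrong to conclude that the primary analysis is compromised. The data entering it are the same under either reading, and the analysis is descriptive. The most that can be said is that later BCVA values might differ, because 9.1.1 lets a patient who stops switch to other anti-VEGF treatment.

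**What to change.** Reconcile Protocol Table 6-2, 6.2.3 and 9.1.1 so that they give one consistent instruction for Table 6-2 laser and PDT, and state how the steroid exception relates to 9.1.1. Which rule applies is for the sponsor to decide. The cost is a wording amendment with the approvals required by Protocol 14.1.

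That may come too late to change any decision. Amendment 2 is dated 30 November 2022 and recruitment ended on its approval; the sponsor's SAP signatures are dated 3 April 2024, 490 days or 70 weeks later. With at most 54 weeks per subject, participation would already have ended by then if approval took no more than about 70 − 54 = 16 weeks. The approval date is not in the documents.

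In that case the remedy belongs in the reporting:

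- Flag patients with Table 6-2 laser or PDT in the q12w-maintenance output, separately from YAG laser, which Protocol 6.2.1.1 permits. SAP 2.4.2 counts and lists any laser treatment, so the source listing already exists.
- Flag them in the interval-prolongation output where early stopping determines the last interval.
- Show the q12w result both ways: once with all flagged patients as non-responders, and once with those stopped solely because of the laser scored on their disease-activity assessments up to stopping. Section 9.1.1 drops the disease stability assessment after discontinuation, so the second version assumes q12w would have continued and should say so.

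The cost is one flag and one extra tabulation.

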6.2.3 Rescue medication

There will be no rescue medication for nAMD in the study eye.

In case of lack of efficacy with investigational drug for nAMD and if the investigator deems it is in the best interest of the patient to receive prohibited treatment ([Section 6.2.2](#)) in the study eye, the investigator should follow the instructions for study treatment discontinuation or study discontinuation provided in [Section 9](#).

6.3 Subject numbering, treatment assignment, randomization

6.3.1 Subject numbering

Each subject is identified in the study by a Subject Number (Subject No., three digits), that is assigned when the subject is first enrolled for screening and is retained as the primary identifier for the subject throughout his/her entire participation in the trial. The Subject No. consists of the Center Number (Center No., four digits) (as assigned by the sponsor to the investigative site) with a sequential subject number suffixed to it, so that each subject is numbered uniquely across the entire database. Upon signing the informed consent form, the subject is assigned to the next sequential Subject No. available in the electronic data capture (EDC) system.

Once assigned to a patient, the patient number will not be reused for another patient. Subjects who have been screen failures but are rescreened (see [Section 8.1](#)) will be assigned a new Subject No. if rescreening occurs beyond 14 days from the original screening date.

If the patient fails to be randomized for any reason, the reason for not being randomized will be entered on the Screening Log, and the Demography eCRF should be completed.

6.3.2 Treatment assignment, randomization

The randomization numbers will be generated using the following procedure to ensure that treatment assignment is unbiased and concealed from subjects and investigator staff. A randomization list will be produced by or under the responsibility of the sponsor using a validated system that automates the random assignment of treatment arms to randomization numbers in the specified ratio. Randomization codes will be assigned by the eCRF. The randomization codes should be requested only after receiving the positive feedback from the reading center (via the eCRF) and central lab (female patients, if applicable) that the patient in screening is eligible to be included in the study as described in [Figure 6-1](#).

Randomization codes and data about all study drug injected to the patient's eye will be tracked in the eCRF.

[figure not shown]

Figure 6-1 Screening and randomization procedure

6.4 Treatment blinding

Treatment will be open to subjects, investigator staff, persons performing the assessments, and the clinical trial team (CTT). The central reading center (CRC) will be blind to the identity of the treatment from the time of randomization until database lock.

6.5 Dose escalation and dose modification

No study treatment dose modification is allowed.

Deviations from dose intervals during the initiation phase and/or dose adjustments during the whole study are not allowed.

Interruption of study treatment is allowed if warranted by an AE.

6.6 Additional treatment guidance

6.6.1 Treatment compliance

The date and time of all study treatment injections administered during the study and any deviations from the protocol treatment schedule will be captured by the investigator staff or by the field monitor on the appropriate study treatment dispensing form.

Exposure to the study treatment will be based on the number of injections administered. Compliance with the study treatment will be assessed by the field monitor at each visit using medication counts and information provided by the investigator / study personnel.

6.7 Preparation and dispensation

Each study site will be supplied with study drug in packaging as described under investigational and control drugs section ([Section 6.1.1](#)).

6.7.1 Handling of study treatment

Study treatment must be received by a designated person at the study site, handled and stored safely and properly and kept in a secured location to which only the investigator and designated

site personnel have access. Upon receipt, all study treatment must be stored according to the instructions specified on the labels and in the IB. Clinical supplies are to be dispensed only in accordance with the protocol. Technical complaints are to be reported to the respective Novartis CPO Quality Assurance.

Medication labels will be in the local language and comply with the legal requirements of each country. They will include storage conditions for the study treatment.

The study personnel must maintain an accurate record of the shipment and dispensing of study treatment in a drug accountability log. Monitoring of drug accountability will be performed by the monitors during site visits or remotely and at the completion of the trial.

At the conclusion of the study, and as appropriate during the course of the study, the study personnel will return all unused study treatment, packaging, drug labels, and a copy of the completed drug accountability log to the Novartis monitor or to the Novartis address provided in the investigator folder at each site.

6.7.2 Instruction for prescribing and taking study treatment

There will be two different treatment regimens (see [Figure 6-2](#)) for IVT injections with different timing for brolucizumab “loading” and “non-loading” treatment arms:

- **Brolucizumab 6 mg “loading”:** Treatment with brolucizumab will be initiated with three loading injections every 4 weeks for three consecutive injections (baseline, weeks 4 and 8). From week 8 onwards, patients will be scheduled to receive one injection of brolucizumab 6 mg every 12 weeks.
- **Brolucizumab 6 mg “non-loading”:** Treatment with brolucizumab will be initiated with one single injection (baseline). From baseline onwards, patients will be scheduled to receive one injection of brolucizumab 6 mg every 12 weeks.

For both study arms:

- The assessment of disease activity will be performed 8 and 12 weeks after the previous injection.
- If disease activity is identified by the investigator for the first time at any visit after / from week 8 respectively, patients should stay on a q12w dosing, if the decline in BCVA is clinically non-significant (BCVA loss \leq 4 ETDRS letters) compared to the previous visit.
- If after / from week 8, a BCVA-loss of \geq 5 ETDRS letters appears compared to the previous visit or disease activity is identified for a second time based on the investigator’s judgement of visual and/or anatomic outcomes and signs of disease activity*, patients must be assigned to q8w dosing.
- One attempt of re-extension to q12w will be allowed based on the investigator’s judgement if no disease activity (DA) is detected during the subsequent visit(s).
- If the patient shows significant DA after the re-extension attempt, injection intervals will be fixed to q8w until the end of the study

- *The disease activity decision should be based on the BCVA loss criterium (BCVA loss ≥ 5 ETDRS letters or ≤ 4 ETDRS letters compared to the previous visit) and beyond that on investigator's judgment of visual and/or anatomic outcomes and signs of disease activity (e.g. IRF, SRF, hemorrhage, leakage, visual acuity loss over time etc.).

[figure not shown]

Figure 6-2 Treatment regimen

Evaluation of Disease Activity (DA):

The concept of the brolucizumab q12w/q8w regimen is to allocate patients according to their individual treatment needs to either a q12w or a q8w treatment schedule. The initial schedule is q12w and a patient will remain on q12w as long as the investigator does not identify nAMD disease activity which in his opinion requires more frequent anti-VEGF treatment (BCVA-loss of ≥ 5 ETDRS letters compared to the previous visit or disease activity is identified for a second time based on the investigator's judgement of visual and/or anatomic outcomes).

In case of BCVA-loss of ≥ 5 ETDRS letters compared to the previous visit, the patient must be switched to a q8w regimen. Beyond the BCVA loss criteria, the assessment of the DA is at the discretion of the investigator and should be made based on changes in vision and anatomical parameters (e.g. IRF, SRF, hemorrhage, leakage, vision loss over time etc.) with reference to the patients' disease status. [Figure 6-3](#) shows three examples for regimen adjustments for the loading arm (examples 1-3) and non-loading arm (examples 4-6), respectively.

[figure not shown]

Figure 6-3 Examples for treatment regimen adjustments

Brolucizumab should be administered in the study eye on the day of the study visit or, if this is not possible, within 3 days after the occurrence of the study visit or no later than within the visit window (± 7 days) as described in [Section 3](#) and [Section 8](#). Every effort should be made to ensure that the subject adheres to the visit/treatment schedule.

When assessments and treatments take place on the same day, treatment must occur after completion of the efficacy assessments described in [Section 8.3](#) and pre-injection safety measures (tonometry, slit lamp and fundus examinations) described in [Section 8.4.3](#). If study visit assessments and the corresponding treatment occur on separate days, a repeat safety checkup should be performed prior to treatment of the eye and results documented in the source documents. If any safety concern arises related to the study eye that, in the opinion of the investigator, may be further impacted by the study treatment or injection procedure, treatment needs to be cancelled.

Brolucizumab administration

The IVT injection procedure for brolucizumab including aseptic and antimicrobial requirements, will be performed according to local clinical practice. IVT injection is contraindicated in

patients with active ocular or periocular infections and in patients with active intraocular inflammation (IOI); therefore, the investigators must verify that these conditions are not present in the study eye prior to every injection. Any adverse events must be recorded in the eCRF.

If any signs of intraocular inflammation are present, then an IVT injection **must not** be performed. Additional ophthalmic examination and imaging should be performed to evaluate IOI (see [Section 8.4.3](#)).

In patients developing intraocular inflammation, including retinal vasculitis and/or retinal vascular occlusion, treatment with brolucizumab in the FALCON study should be discontinued and the events should be promptly managed.

7 Informed consent procedures

Eligible subjects may only be included in the study after signing Institutional Review Board/Independent Ethics Committee (IRB/IEC)-approved informed consent.

Informed consent must be obtained before conducting any study-specific procedures (e.g. all of the procedures described in the protocol) and collecting any study-relevant information. The process of obtaining informed consent must be documented in the subject source documents.

Novartis will provide to investigators in a separate document a proposed informed consent form that complies with the International Council on Harmonization Good Clinical Practice (ICH) GCP guidelines and regulatory requirements and is considered appropriate for this study. Any changes to the proposed consent form suggested by the investigator must be agreed by Novartis before submission to the IRB/IEC.

Information about common side effects already known about the investigational drug can be found in the Investigator's Brochure (IB). This information will be included in the subject informed consent and should be discussed with the subject during the study as needed. Any new information regarding the safety profile of the investigational drug that is identified between IB updates will be communicated as appropriate, for example, via an investigator notification or an aggregate safety finding. As new information becomes available, informed consent to be updated and then must be discussed with the subject.

Women of child-bearing potential must be informed that taking the study treatment may involve unknown risks to the fetus if pregnancy were to occur during the study and agree that in order to participate in the study they must adhere to the contraception requirements for the duration of the study and for 3 months after stopping the investigational medication.

If there is any question that the patient will not reliably comply, they must not be entered in the study.

A copy of the approved version of all consent forms must be provided to Novartis after IRB/IEC approval.

During the COVID-19 pandemic that may challenge the ability to obtain a standard written informed consent due to limits that prevent an on-site visit, the investigator may conduct the informed consent discussion remotely (e.g. telephone, videoconference). Guidance issued by local regulatory bodies on this aspect prevail and must be implemented and documented (e.g. the presence of an impartial witness, sign/dating separate ICFs by trial

participant and person obtaining informed consent, etc.). Remote informed consent should be appropriately documented and confirmed by way of standard informed consent procedures at the earliest opportunity when the subject will be back at the trial sites.

8 Visit schedule and assessments

The assessment schedule ([Table 8-1](#)) lists all the assessments when they are performed (indicated with an “X”). All data obtained from these assessments must be supported in the subject’s source documentation. All data must be entered in the eCRF in a timely manner (see [Section 11.1](#)).

Subjects should be seen for all visits/assessments as outlined in the assessment schedule ([Table 8-1](#)). All post-baseline and/or subsequent scheduled visits will be calculated based on the day 1 visit date. From baseline on, patients will visit the site every 4 weeks. From baseline (non-loading arm) or week 8 (loading arm) to week 52, the treatment intervals will be set to q12w / q8w by the investigator, based on the patient’s disease activity (see [Section 6.7.2](#)). All efforts should be made to adhere to all scheduled visits and assessments as outlined in the assessment schedule ([Table 8-1](#)).

A \pm 7-day visit window is allowed, except for baseline/day1 and the week 52 visit (\pm 21-day visit window), should the subject be unable to return per scheduled visit. For a given protocol visit, assessments can be performed on two consecutive days in which both days must occur within the \pm 7-day visit window.

Treatment is intended to be administered on the day of study visit, or if this is not possible, within 3 days after the study visit at which the per-protocol assessments took place. For all visits, efficacy assessments ([Section 8.3](#)) and safety assessments ([Section 8.4](#)) should be performed prior to any administration of study treatment.

Missed or rescheduled visits should not lead to automatic discontinuation. Subjects who prematurely discontinue the study for any reason should be scheduled for a visit as soon as possible, at which time all of the assessments listed for the final visit will be performed. At this final visit, all dispensed investigational product should be reconciled, and the adverse event and concomitant medications recorded on the CRF.

If the COVID-19 pandemic limits or prevents on-site study visits, study treatment could not be administered and other study assessments may not be performed. Alternative methods of safety monitoring may be implemented. Depending on local regulations, site capabilities and patient’s visit status in the study, phone calls or virtual contacts (e.g. teleconsult) can be performed for safety follow-up for the duration of the pandemic, until it is safe for the participant to visit the site again.

Table 8-1 Assessment schedule

